4.8 Study Stopping Rules

We may terminate this study at any time after informing the IND office. Conditions that may warrant termination of the study include, but are not limited to the following:

- Upon the emergence of an unexpected, serious, or unacceptable risk to the patients in the study.
- Grade 3/4 toxicity rate > 30% (See details in section 7. STATISTICAL ANALYSIS PLAN)
- Upon the observation of the inefficacy in the phase 2 part. The BOP2 design in the phase 2 part has an early stopping rule: if we observed less than 2 clical benefits in 12 patients, we will stop the study for futility.
- A decision on the part of the IKENA Oncology to suspend or discontinue testing, evaluation, or development of the grapiprant.

Protocol 2021-0077 Proprietary Information of MD Anderson PI: [name]

Co-PI: [name] Date: 11/22/2022

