Phase II adopts the Bayesian optimal phase II (BOP2) design with the null hypothesis H0: CBR = 10% versus the alternative hypothesis H1: CBR = 30%. If the phase II part starts with 300 mg dosing, we will enroll 6 patients and evaluate the clinical benefit in 12 patients (including 6 patients from the phase Ib cohort). For the purpose of futility monitoring, the assessment window for CBR is 24 weeks. If we observed 2 or more clinical benefits in 12 patients, we will proceed to enroll 13 patients and claim the study promising if we observed 5 or more clinical benefits in 25 patients. This design yields the power of 86% with the type I error of 10%.

If the phase II part starts with 200 mg dosing, we will enroll 5 patients and evaluate the clinical benefit in 11 patients (including 6 patients from the phase Ib cohort). If we observed 2 or more clinical benefits in 11 patients, we will proceed to stage 2. For stage 2, (a) if 3 patients treated at 300mg, we will enroll additional 11 patients, and we claim the study promising if we observed 4 or more clinical benefit in 22 (or 19) patients; and (b) if 6 patients treated at 300mg, we will enroll additional 8 patients and we claim the study promising if we observed 4 or more clinical benefit in 19 patients. The power of the design is 86% and 82%, respectively in case (a) and (b), given the type I error of 10%. The operating characteristics for the phase II portion of the trial are summarized in the **Table 7** below:

Table 7: The Operating Characteristics for Phase II

Scenario	Clinical Benefit Rate	Early Stopping (%)	Claim Promising (%)	Average Number of Patients (%)
1	0.1	65.9	8.3	16.4
2	0.2	27.5	52.0	21.4
3	0.3	8.5	86.4	23.9

Co-PI: [name] Date: 11/22/2022

[figure not shown]
Scenario	Clinical Benefit Rate	Early Stopping (%)	Claim Promising (%)	Average Number of Patients (%)
4	0.4	2.0	97.5	24.7
5	0.5	0.3	99.7	25.0

Product: Grapiprant Protocol 2021-0077 Proprietary Information of MD Anderson PI: [name]

Co-PI: [name]

Date: 11/22/2022

Figure 2. Trial design for phase Ib/II of grapiprant and eribulin treatment

Co-PI: [name] Date: 11/22/2022

The CBR and ORR will be summarized by frequency and percentage with 95% exact confidence intervals for all patients and by doses. Time to progression (TTP), progression-free survival (PFS), and overall survival (OS) will be summarized using the Kaplan-Meier method, including median with 95% confidence intervals.

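### Section 4.8 gives one futility look at 12 patients for all of phase II, whereas section 7.0 places the look at 11 patients if phase II runs at 200 mg

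*Combined protocol and SAP*

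**What the plan says.** Section 4.8 (Study Stopping Rules) lists conditions that may lead to termination. The bullet on inefficacy covers the phase 2 part as a whole and gives the rule as "if we observed less than 2 clical benefits in 12 patients, we will stop the study for futility". It names no dose. The toxicity bullet in the same list points to section 7; this one does not.

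Section 7.0 (Statistical Analysis Plan) makes the look depend on the dose:

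- 300 mg: "If the phase II part starts with 300 mg dosing, we will enroll 6 patients and evaluate the clinical benefit in 12 patients", 6 of them carried over from phase Ib. Two or more benefits lead to 13 further patients, and the plan will "claim the study promising if we observed 5 or more clinical benefits in 25 patients".
- 200 mg: "we will enroll 5 patients and evaluate the clinical benefit in 11 patients (including 6 patients from the phase Ib cohort"), followed by "If we observed 2 or more clinical benefits in 11 patients, we will proceed to stage 2". Stage 2 then adds 11 patients in case (a), where 3 patients had been treated at 300 mg, or 8 in case (b), where 6 had. A claim needs 4 benefits, in 22 or 19 patients respectively.

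The reporting schedule at the end of section 7.0 repeats the difference: the first efficacy summary is due after 12 evaluable patients if the MTD is 300 mg and after 11 if it is 200 mg.

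**The concern.** A stopping rule should read the same wherever it appears. Here the section headed as the stopping rules gives a threshold that the SAP applies in only one of two branches. Suppose phase II runs at 200 mg and 11 patients have yielded 1 benefit. Section 7.0 does not proceed to stage 2. Section 4.8 as written gives no stop until a 12th patient has been evaluated, which means one more treated patient and up to another 24-week assessment window. The stated power and type I error for the 200 mg branch were also given for an 11-patient look, so it is worth asking how far a 12-patient look would move them.

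**Working it through.** **Inputs, all from section 7.0 unless noted.** Hypotheses: "null hypothesis H0: CBR = 10% versus the alternative hypothesis H1: CBR = 30" per cent. 300 mg: continue with at least 2 of 12, claim with at least 5 of 25. 200 mg: continue with at least 2 of 11, claim with at least 4 of 22 in case (a) or 4 of 19 in case (b). Stated power is 86% in (a) and 82% in (b), with type I error 10%. Section 4.8: stop with fewer than 2 of 12.

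**Formulas.** With stage 1 size n1, total n, claim cutoff r and benefit rate p:

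- P(early stop) = P(X1 ≤ 1), X1 ~ Bin(n1, p)
- P(claim) = Σ over x ≥ 2 of P(X1 = x) · P(Bin(n − n1, p) ≥ r − x)

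**Step 1. Reproduce the plan's figures for 300 mg.** (n1, n, r) = (12, 25, 5) gives early stopping 65.9%, type I error 8.3% and mean sample size 16.4 at p = 0.10, and power 86.4% at p = 0.30. These match Table 7, so the method is the plan's. The accompanying text, "This design yields the power of 86% with the type I error of 10" per cent, therefore uses 10% as a ceiling.

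**Step 2. How often the two rules disagree at 200 mg.**

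- At p = 0.10: P(0 of 11) = 0.9^11 = 0.3138; P(1 of 11) = 11 × 0.1 × 0.9^10 = 0.3835. Early stopping with the 11-patient look is 0.3138 + 0.3835 = 0.6974 (sum of unrounded terms).
- With 0 of 11, a 12th patient cannot bring the count to 2, so the outcome is the same under either rule.
- With 1 of 11, the rules differ in immediate action. They differ in outcome only if patient 12 benefits: 0.3835 × 0.10 = 0.038.
- Cross-check: early stopping with the 12-patient look is 0.9^12 + 12 × 0.1 × 0.9^11 = 0.2824 + 0.3766 = 0.6590, and 0.6974 − 0.0384 = 0.6590.
- At p = 0.30: P(1 of 11) = 11 × 0.3 × 0.7^10 = 0.0932, and 0.0932 × 0.30 = 0.028.

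**Step 3. Effect on case (b), at least 4 of 19.** At p = 0.10:

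- 11-patient look: 0.2131 × 0.1869 + 0.0710 × 0.5695 + P(X1 ≥ 4) = 0.0398 + 0.0404 + 0.0185 = 0.0988 (rounded terms)
- 12-patient look: 0.2301 × 0.1497 + 0.0852 × 0.5217 + P(X1 ≥ 4) = 0.0344 + 0.0445 + 0.0256 = 0.1046 (rounded terms)

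| Case (b) | Look at 11 | Look at 12, total still 19 |
|---|---|---|
| Type I error | 9.88% | 10.46% |
| Power | 82.12% | 84.00% |
| Early stopping, CBR 10% | 69.7% | 65.9% |

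If the 8 stage 2 patients were kept after a 12-patient look (4 of 20), type I error would be 11.7%. The documents describe no such design.

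**Step 4. The same check on case (a), at least 4 of 22.**

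- 11-patient look: 0.2131 × 0.3026 + 0.0710 × 0.6862 + 0.0185 = 0.1318 (sum of unrounded terms); power 85.94%
- 12-patient look, total still 22: type I error 14.19%, power 88.32%

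The stated 86% power reproduces. The stated 10% error does not, with either look. A cutoff of 5 in 22 with the 11-patient look would give 5.4% error and 79.1% power, so it would not deliver the stated 86%.

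**The case against.** The best defence is that section 4.8 is a summary. Its list is expressly not exhaustive and allows termination at any time, so stopping at 11 under section 7.0 would not breach it. Section 4.3 sends the reader to section 7.0 for the detail of the design, and the synopsis likewise gives only the 300 mg efficacy rule. This lowers the risk but does not remove it. The futility bullet says the study will stop, gives an exact threshold, applies it to the phase 2 part without qualification, and carries no cross-reference.

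The defence succeeds against several stronger readings that a reader might draw:

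- **That a 12-patient look breaks the 10% error across the 200 mg branch.** In case (b) the shift is 0.6 point and 10.46% still rounds to the stated 10%. In case (a) the error exceeds 10% under section 7.0's own 11-patient look, so section 4.8 is not the cause.
- **That 38% of trials would end with a different decision.** That is the share in which the rules call for different action at patient 11. Most of those trials stop one patient later anyway.
- **That 300 mg patients might be counted in the 200 mg look.** Section 4.8 is silent, but section 7.0 builds the 11 from 5 new patients and 6 from phase Ib, and its reporting schedule specifies 6 treated at the MTD.

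**Conclusion.** The inconsistency is real: section 4.8 conflicts with section 7.0 on the futility threshold if phase II runs at 200 mg. Its practical size is modest. The rules call for different action at patient 11 in 38% of trials at CBR 10% (9.3% at CBR 30%), and lead to a different stop or continue outcome in 3.8% and 2.8%. In case (b) the operating characteristics barely move. This is a consistency error in a decision rule and not a failure of error control.

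The figures assume independent patients with a common benefit rate, full evaluability, and totals held at 22 or 19. For case (a), 22 is used because 11 + 11 = 22 and it reproduces the stated power; the text there reads 22 (or 19), which is itself unclear. It would be wrong to infer that aligning section 4.8 secures the 10% error throughout the 200 mg branch, since case (a) stays at 13.2%.

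**What to change.** Reconcile the futility bullet in section 4.8 with section 7.0. Either state both looks (fewer than 2 clinical benefits in 12 patients if phase II runs at 300 mg, fewer than 2 in 11 if it runs at 200 mg, counting patients treated at the selected phase II dose), or replace the numbers with a reference to section 7.0. The cost is one sentence in the next amendment, with no change to sample size or analysis.

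Separately, the statistician should revisit the case (a) rule and its stated error, clarify which total applies, and add operating characteristics for the 200 mg branch, since Table 7 covers only the 300 mg design.

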4.9 Criteria for Disease Control

This study aims to determine the safety and efficacy of grapiprant combination treatment in patients with mIBC. PI will be responsible for monitoring safety and disease control status. Detail of the adverse event and the evaluation of disease status will be documented and recorded in the study-specific database.

4.9.1. Definition of Treatment Response

We will perform imaging analysis by CT scan, bone scan, or PET-CT. If the patient had a locoregional disease, a mammogram and ultrasound would be considered. We will evaluate the treatment response in metastasis sites (and primary site, if it exists) and at the following time points: 1) baseline 2) after 2 cycles of proposed treatment (does not include window period) 3) every 3 cycles of proposed treatment. All imaging analysis will be performed based on RECIST criteria. The efficacy outcomes will be CBR, ORR, Time to progression (TTP), Progression-free survival (PFS), and overall survival (OS).

4.9.2. Response will not be considered evaluable in the following categories:

Patients have to receive at least 2 cycles of the combination of eribulin and grapiprant to be evaluated the response. The patients in the following categories are considered to be unevaluable for the response. Those patients who are not evaluable will be excluded from the response's statistical analysis and not be replaced.

Early Deaths:

Patients who die within the first 2 weeks of the initiation of proposed treatment. These cases will be considered treatment failures.

Lost to Follow-up:

Patients for whom there is inadequate information to judge tumor response because of loss of contact with our institution (> 2 months after a missed appointment) and referring physician despite repeated attempts to locate them. These cases will be considered treatment failures in the intent-to-treat analysis.

Major Protocol Violation:

Patients who significantly deviate from the treatment program by either adding or deleting another agent or another therapeutic maneuver or modifying the schedule substantially (delay treatment ≥ 7 days without administration reason) of the drug under evaluation. Patients who do not fulfill the requirements outlined under patient eligibility are also included in this category.

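### Section 4.9.2 both excludes unevaluable patients and counts some of them as failures, so the set behind the primary CBR and its go/no-go counts is not fixed; separately, the 200 mg case (a) rule has 13.2% type I error, not 10%

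*Combined protocol and SAP*

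**What the plan says.** Section 4.9.2 opens with a condition: "Patients have to receive at least 2 cycles of the combination of eribulin and grapiprant to be evaluated the response". On handling, it says "Those patients who are not evaluable will be excluded from the" response "statistical analysis and not be replaced". It then lists three unevaluable categories: early deaths, losses to follow-up and major protocol violations (which include ineligible patients). For early deaths it adds "These cases will be considered treatment failures". For losses it adds "These cases will be considered treatment failures in the intent-to-treat analysis". Section 7.0 contains no intent-to-treat set.

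Section 7.0 states the 300 mg rule as at least 2 benefits in 12 patients to continue, then at least 5 in 25. Section 4.8 repeats the 12-patient rule. For reporting, "The CBR and ORR will be summarized by frequency and percentage with 95% exact confidence intervals for all patients and by doses". Later, Section 7.0 ties the efficacy summaries to 12 (300 mg) or 11 (200 mg) evaluable patients and then to 25 evaluable patients. The last 200 mg summary waits for 24 cycles. Sections 4.3 and 7.0 cap the study at 25 patients.

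On the 200 mg path, case (a), "we claim the study promising if we observed 4 or more clinical benefit in 22 (or 19) patients". For cases (a) and (b) together, "The power of the design is 86% and 82%, respectively in case (a) and (b), given the type I error of 10" per cent.

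**The concern.** CBR is a primary outcome and drives both go/no-go decisions. A patient cannot be outside the denominator and also a failure within it. Someone who stops before two cycles for progression or toxicity fits none of the three listed categories, fails the two-cycle condition, and so drops out on a plain reading of Section 4.9.2. Such patients are among the least likely to have had clinical benefit. Removing them conditions the estimate on events after treatment start, in an uncontrolled trial judged against a 10% null. For protocol violators and ineligible patients the direction is open, because some may have benefited. In that case the exclusion changes the count as well as the percentage.

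The triggers raise a related question. If evaluable in the Section 7.0 reporting schedule has its Section 4.9.2 meaning, one exclusion puts 25 evaluable patients out of reach under a cap of 25 with no replacement.

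**Working it through.** **1. Reproduce the stated design.** Inputs from Section 7.0: CBR 10% under H0 and 30% under H1; continue with at least 2 of 12; promising with at least 5 of 25. The exact two-stage probability is

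P(promising) = Σ over x ≥ 2 of Bin(x; 12, p) × P[Bin(13, p) ≥ 5 − x].

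This gives 8.33% at p = 0.10 and 86.35% at p = 0.30, matching Table 7 (8.3% and 86.4%). These figures assume that all 12 and all 25 patients count.

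**2. Effect on the reported CBR.** Hold five benefits fixed and drop patients without benefit. The documents give no exclusion rate, so 3 and 5 exclusions are assumptions. Exact (Clopper-Pearson) 95% intervals:

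- 5/25 = 20.0% (6.8 to 40.7)
- 5/22 = 22.7% (7.8 to 45.4)
- 5/20 = 25.0% (8.7 to 49.1)

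**3. Effect on the 300 mg decision rule.** Assume 25 enrolled, each excluded with probability q, so that the evaluable number is M ~ Bin(25, 1 − q). The interim falls at the 12th evaluable patient, cutoffs stay at 2 and 5, and results are averaged over M. The all-patient CBR is p.

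- If every excluded patient is a failure, the rate among evaluable patients is p/(1 − q). At q = 10%, 20% and 30%, type I error is 8.8%, 9.2% and 9.5%, and power is 88.5%, 90.0% and 90.7%. Type I error cannot exceed the single-look value P[Bin(25, 0.10) ≥ 5] = 9.8%.
- If exclusion is independent of benefit, the rate among evaluable patients stays at p and there are fewer of them. Power is 81.5%, 73.5% and 62.1% at the same q, and type I error is below 8.3%.

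**4. The trigger of 25.** The chance that all 25 enrolled are evaluable is (1 − q)^25: 27.7%, 7.2% and 0.4% at q = 5%, 10% and 20%. This applies only if evaluable has its Section 4.9.2 meaning.

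**5. The 24 cycles.** With 21-day cycles, 24 × 3 = 72 weeks, against the 24-week CBR window in Section 7.0.

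**6. The 200 mg rules, with no exclusions.** Case (a) has 6 + 5 + 11 = 22 patients and case (b) has 6 + 5 + 8 = 19. For case (a), 2/11 then 4/22 at p = 0.10:

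- exactly 2 of 11, then at least 2 of 11: 0.2131 × 0.3026 = 0.0645
- exactly 3 of 11, then at least 1 of 11: 0.0710 × 0.6862 = 0.0487
- at least 4 of 11: 0.0185
- sum, before rounding of terms: 13.2%; power at p = 0.30 is 85.9%

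Case (b), 2/11 then 4/19, gives 9.9% and 82.1%. The stated powers of 86% and 82% therefore reproduce, and the stated 10% holds for case (b) only.

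**The case against.** The best defence is that the cutoffs are absolute counts. If looks fall at 12 and 25 enrolled and the excluded patients had no benefit, dropping them or counting them as failures gives the same decision. Only the percentage moves, by 2.7 to 5.0 points, inside intervals about 34 to 40 points wide. That stands for this scenario, but not if patients with benefit are removed as protocol violators.

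A second defence is that the plan is not silent: Section 4.9.2 excludes, and Section 7.0 refers to all patients. It is right that a reader who infers silence goes too far. The fault is conflicting statements. The reference to all patients does not resolve them, since beside by doses it may mean only pooled over doses.

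Third, evaluable in the reporting schedule may not mean the two-cycle set: the same text uses it for patients completing one cycle. On the 200 mg path, 25 may be the whole-trial total (3 + 22 or 6 + 19). Both points stand. The documents therefore do not support calling the 200 mg trigger unreachable. The 24 cycles may be a slip for 24 weeks but still needs correcting.

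Fourth, an all-treated set has its own gap: Section 5.2 foresees patients sampled but never dosed, so 25 treated may not be reached. This is a smaller problem. With 12 then 24 counted patients and the cutoffs kept, type I error is 7.4% and power 84.9%.

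**Conclusion.** The point holds as a conflict over the analysis set and should be fixed. Following the exclusion as written biases the CBR upward when the dropped patients had no benefit. The size, from 20.0% to 22.7% or 25.0% with five benefits, rests on assumed exclusion counts.

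A reader might infer that exclusion inflates type I error. With 25 enrolled and the 300 mg cutoffs kept, it does not: it stays below 10%. Inflation on that path would need enrolment beyond the cap (for example 10.8% with looks at 13 and 27 enrolled, excluded patients counted as failures), which the cap and the no-replacement rule do not allow. A reader might equally infer that power is safe. That holds only if all excluded patients are failures. If exclusion is independent of benefit, power falls to 81.5%, 73.5% or 62.1% at assumed rates of 10%, 20% or 30%. The documents do not say which applies.

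The 200 mg case (a) error is separate and depends on no assumption about exclusions: 13.2% against the stated 10%. It does not follow that the sponsor must accept either 13.2% or about 79% power, as other boundaries exist.

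**What to change.** - In Sections 4.9.2 and 7.0, define one set for the primary CBR, ORR and the go/no-go counts: all patients at the phase II dose level who received at least one dose of study treatment, including rolled-over phase Ib patients. Count those without a qualifying assessment (early death, loss, under two cycles) as no clinical benefit.
- State in advance whether patients who stop in the window period before eribulin count, and how the counts apply if an enrolled patient is never dosed.
- Keep the evaluable set as a labelled supportive analysis. Do not call the all-treated set intent-to-treat.
- Apply 2/12 and 5/25 to the all-treated set. With 12 and 25 treated patients this keeps 8.3% and 86.4%, read as rates among all treated patients.
- Reword the efficacy triggers to the decision samples (12 and 25; 11 and 22 or 19), each patient having completed 24 weeks of follow-up or earlier progressed, died or discontinued. Reconcile the 24 cycles with the 24-week window.
- In case (a), replace the double figure with 22. Either restate type I error as 13.2%, or choose another boundary and state its figures: for example, 2/11 then 5/22 gives 5.4% and 79.1% power, and 1/11 then 5/22 gives 6.1% and 83.1%.

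The cost is protocol and SAP wording, with no added patients or procedures. The reported CBR may be a few points lower, and the stated case (a) figures become less favourable: a higher type I error, or lower power under either example boundary.

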4.10 Follow Up after off treatment

30-day safety follow up

The mandatory Safety Follow-Up should be conducted approximately 30 days after the last dose of the proposed treatment or before initiating a new anti-cancer treatment, whichever comes first. All Product: Grapiprant

Protocol 2021-0077 Proprietary Information of MD Anderson

PI: [name] Co-PI: [name] Date: 11/22/2022

AEs that occur before the safety follow-up visit should be recorded. Safety follow-up can be done in the clinic or by phone if the patient cannot visit the clinic for follow-up.

Patients who have an ongoing major study treatment related AE when the study treatment is completed or at discontinuation from the study will be followed up to 30 days until the event has resolved to baseline grade, the event is assessed by the investigator as stable, new anticancer treatment is initiated, the patient is lost to follow-up, the patient withdraws consent, or until it has been determined that study treatment or participation is not the cause of the AE.

Survival Follow Up (yearly up to 5 years)

The survival follow-up can be performed yearly for up to 5 years; if the patient is unable to visit the clinic, the follow-up will be done by chart review or by phone.

4.11 Remote Procedures

In case of any unexpected incidents that patients can't come back to MD Anderson Cancer Center for study treatment and assessments, remote procedures can be applied for this trial conduction, including remote consent, remote toxicity assessment via phone calls, virtual visit, etc., with compliance with institutional policies. Patients can have lab work, scheduled scans, physical exams and receive treatment locally if applicable. Laboratory work done at an outside facility is to be forwarded to the subject's attending physician at MDACC or the PI of the study, who will date and sign off on the labs to verify the results were reviewed. If the patient's outside records are available to review in MDACC's EMR (i.e. EPIC 'Care Everywhere'), then it will be documented in either the physician's note and/or the study coordinator's note (attested by the physician) that the outside labs, infusions and other assessments were reviewed by the MDA attending physician. Remote monitoring can be applied as needed. Study drug may be mailed to the patient per institutional guidelines/approval.

